4.1.2. Part 2: Open-Label Randomized

The open-label, randomized portion (Part 2) of the study will begin after an initial safety evaluation of at least 40 subjects from Part 1. Prior to the initiation of Part 2, the protocol will be revised with the dosing regimen selected from Part 1 and will include adequate justification to support the proposed dose/schedule in Part 2.

During Part 2, subjects are randomized in a 1:1 ratio to the 2 treatment arms, stratified by international prognostic index (IPI) risk score at baseline (Sehn, 2007; 3 to 5 versus 0 to 2), number of lines of prior therapy (1 versus ≥ 2), and primary refractory (yes versus no). Primary refractory enrollment is limited to 36 of 200 subjects. Part 2 will enroll approximately 200 subjects. The sample size for Part 2 may be adjusted based on the results from Part 1. An increase in the enrollment number beyond 200 will be made by a protocol amendment prior to the initiation of the randomized portion. An independent data monitoring committee (IDMC) will review safety data during Part 2 with meetings scheduled after 50, 100, and 150 subjects have been randomized. The primary analysis for PFS will occur after 89 disease progression and death events. An interim analysis for OS will be performed at that time (see Section 11.3).

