11.3. Sample Size and Power

11.3.1. Progression-Free Survival

PFS as assessed by the BIRC is the primary endpoint for Part 2 of this study. For determination of the sample size, it is assumed that triple combination treatment could improve the median PFS from 12 months (under treatment with tafasitamab + lenalidomide (Duell, 2021) to 23.5 months under the triple combination treatment (plamotamab + tafasitamab + lenalidomide), corresponding to a hazard ratio (HR) of 0.51 with all randomized subjects (it is estimated that 90% of subjects will be central pathologically confirmed as DLBCL).

The log rank test has 90% power with the sample size of 200 (93 events) to preserve the type-I error of 0.025 (one-sided). A loss to follow-up rate of 1.5%/month was assumed for sample size calculations.

Subjects will be randomized 1:1, stratified by IPI risk score at baseline (3 to 5 versus 0 to 2), number of lines of prior therapy (1 versus ≥ 2), and primary refractory (yes versus no). A maximum of 36 primary refractory subjects may be enrolled into the sample size of 200.

Enrollment of 200 subjects is estimated to require 27 months with minimum follow-up time of 6 months. The primary efficacy analysis will occur when 93 PFS events per independent review have been observed. Efficacy boundaries and estimated timing for the analysis is displayed in [Table 21](#).

Table 21: Efficacy Boundaries and Properties for Progression-Free Survival Analyses

Analysis	Value	Efficacy
Final	Z	1.9600
N: 200	p (1-sided)	0.0250
Events: 93	HR at bound	0.6659
Month: 33	P(Cross) if HR = 1	0.0250
	P(Cross) if HR = 0.51	0.9000

p (1-sided) is the nominal α for testing.

HR at bound is the approximate HR required to reach an efficacy bound

P(Cross if HR = 1) is the probability of crossing a bound under the null hypothesis

P(Cross if HR = 0.5) is the probability of crossing a bound under the alternative hypothesis

HR = hazard ratio.

An interim analysis for OS at the time of final PFS analysis will be implemented using the group sequential design in addition to the final OS analysis. [Table 22](#) provides the timing of PFS and OS analysis.

Table 22: Summary of Interim and Final Analyses Strategy

Analyses	Key Endpoints	Timing	Estimated Time after First Subject Randomized	Primary Purpose of Analysis

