PFS Final OS IA1	PFS ORR OS TTF	93 PFS event and approx. 50 OS events (65% of expected total OS events) have been observed	Approx. 33 months	
 Final analyses for PFS, ORR, and TTF Interim OS analyses
Final OS Analysis	OS	When approx. 76 OS events have been observed	Approx. 51 months	
 Final OS analyses

ORR = objective response rate; OS = overall survival; PFS = progression-free survival; TTF = time to treatment failure.

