5. STATISTICAL CONSIDERATIONS

5.1. Determination of Sample Size

PFS as assessed by the BIRC is the primary endpoint for Part 2 of this study. For determination of the sample size, it is assumed that triple combination treatment could improve the median PFS from 12 months (under treatment with tafasitamab + lenalidomide to 23.5 months under the triple combination treatment (plamotamab + tafasitamab + lenalidomide), corresponding to a hazard ratio (HR) of 0.51 with all randomized subjects (it is estimated that 90% of subjects will be central pathologically confirmed as DLBCL).

The log rank test has 90% power with the sample size of 200 (93 events) to preserve the type-I error of 0.025 (one-sided). A loss to follow-up rate of 1.5%/month was assumed for sample size calculations.

Subjects will be randomized 1:1, stratified by IPI risk score at baseline (3 to 5 versus 0 to 2), number of lines of prior therapy (1 versus ≥ 2), and primary refractory (yes versus no). A maximum of 36 primary refractory subjects may be enrolled into the sample size of 200.

Enrollment of 200 subjects is estimated to require 27 months with minimum follow-up time of 6 months. The primary efficacy analysis will occur when 93 PFS events per independent review have been observed.

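### The primary PFS analysis has two triggers, 89 and 93 events; only 93 reproduces the stated 90% power, boundary and timing

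*Protocol*

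**What the plan says.** Two event counts are attached to the same analysis.

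**89 events.** Protocol 4.1.2 reads: "The primary analysis for PFS will occur after 89 disease progression and death events". The Methodology part of the protocol synopsis and SAP 3.1.2 carry the same sentence. All three places schedule the OS interim analysis for that same time.

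**93 events.** Protocol 11.3.1 reads: "The primary efficacy analysis will occur when 93 PFS events per independent review have been observed". SAP 5.1 repeats this. Table 22 of the protocol and the corresponding table in SAP 5.2 give the timing as "93 PFS event and approx. 50 OS events (65% of expected total OS events) have been observed".

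The power statement goes with 93 in both documents. Protocol 11.3.1 says "The log rank test has 90% power with the sample size of 200 (93 events) to preserve the type-I error of 0.025 (one-sided"), and SAP 5.1 says the same. The effect size is given as medians of 12 and 23.5 months, "corresponding to a hazard ratio (HR) of 0.51 with all randomized subjects". Table 21, which appears only in the protocol, lists 93 events, month 33, Z = 1.9600, an HR at the bound of 0.6659, and 0.9000 probability of crossing at HR 0.51. Its footnote, however, reads "P(Cross if HR = 0.5) is the probability of crossing a bound under the alternative hypothesis".

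**The concern.** An event-driven trial needs one event count for its primary analysis. Here that count fixes the cut-off for the final PFS, ORR and TTF analyses and for the OS interim. ORR, OS and TTF are tested in sequence only if PFS is positive (protocol 11.3.4), so all confirmatory testing depends on it.

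The two counts cannot be two planned looks: Table 21 has a single, final PFS row, and no alpha is set aside for another. Protocol 4.1.2 itself refers to Section 11.3 when it describes the OS interim, and that section says 93.

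The study is open-label. With two written triggers, either cut-off could be defended after data had been seen. If 89 were used, the power and boundary hazard ratio printed in the protocol would not be those of the analysis performed. The 89-event sentence also does not say that the events are those of the independent review, whereas the 93-event sentence does.

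**Working it through.** **Inputs (protocol 11.3.1):** HR 0.51; medians 12 and 23.5 months; one-sided alpha 0.025 (z = 1.960); 90% power (z = 1.2816); 1:1 allocation; 200 subjects over 27 months plus 6 months' minimum follow-up; 1.5% per month loss to follow-up. The documents do not name the events formula. The Schoenfeld formula is used because it reproduces the plan's figure.

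**1. The plan's own figure.** Events = 4(1.960 + 1.2816)² / (ln 0.51)² = 42.03 / 0.4534 = 92.7, so 93. With the ratio of medians, 12/23.5 = 0.5106, the unrounded value is 93.05. The 93 is reproduced.

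**2. Power at each count.** Power = Φ(½√d × 0.6733 − 1.960), where 0.6733 = −ln 0.51.
- d = 93: Φ(3.247 − 1.960) = 90.1%
- d = 89: Φ(3.176 − 1.960) = 88.8%

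Using 0.5106 instead gives 90.0% and 88.7%.

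**3. Hazard ratio at the boundary.** HR = exp(−2 × 1.960/√d).
- d = 93: 0.6660
- d = 89: 0.6600

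Table 21 prints 0.6659. Solving back, that corresponds to d = 92.94, which is 93 before rounding and not 89.

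**4. Calendar time.** Assume exponential times, uniform accrual over 27 months and 100 subjects per arm. With λ = ln 2/median, η = 0.015 and s = λ + η, expected events per arm by month T are

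100 × (λ/s) × [1 − (e^(−s(T−27)) − e^(−sT)) / (27s)].

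| Month | Control arm | Triple arm | Total |
|---|---|---|---|
| 31.5 | 54.3 | 34.7 | 89.1 (from unrounded values) |
| 33 | 56.9 | 36.7 | 93.7 (from unrounded values) |

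The 89th event is expected at month 31.5 and the 93rd at month 32.8. Only the latter fits the stated month 33. Under the plan's OS assumptions, about 45 deaths are expected at the earlier time and 47 at the later.

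**5. Worst case for type I error.** Suppose PFS were tested at 89 events and, failing that, again at 93, each time against Z = 1.96. The two statistics have correlation √(89/93) = 0.978, and the probability that at least one crosses under the null is 2.98%, against the nominal 2.5%.

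**6. Where 89 may come from.** At HR 0.50 the formula needs 87.5 events, so 88, and 89 events give 90.5% power. Exactly 90% at 89 events corresponds to exp(−2 × 3.2415/√89) = 0.503. Together with the HR 0.5 in the Table 21 footnote, this suggests a remnant of an earlier assumption, but it is inference only.

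**The case against.** The strongest objection is that nothing can now go wrong. The SAP (sections 1, 4.1 and 7) records early termination with 3 subjects enrolled and only listings to be produced. There will be no PFS analysis at either count. The protocol also had to be revised before Part 2 to insert the selected dose, so nobody would have been randomized under this text unrevised. Both statements are true, and they remove the practical consequence. They do not remove the contradiction: the pre-Part 2 revision was not stated to cover the event count, and the SAP written after termination still carries both numbers.

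Other points have partial force:

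- **Testing threshold.** For a single look, Z = 1.96 and the 2.5% error rate are the same at 89 events as at 93. What changes is the boundary hazard ratio, by 0.006, and the power, by 1.3 points. Both changes are small, and the table calls the boundary hazard ratio approximate.
- **Type I error of 3.0%.** It requires two tests at full alpha, which neither document plans. It is a ceiling on misuse, not an expected value.
- **Independent review.** BIRC-assessed PFS is defined as primary elsewhere, including protocol 4.2.1 and Table 20, so the short sentence can be read correctly. Its omission is a minor point.
- **OS events.** Neither trigger reaches the approximately 50 deaths of Table 22 at its expected date, so that shortfall is not caused by 89. The OS bounds come from a spending function, which can adapt to the information actually available.
- **Origin of 89.** At HR 0.50 the formula gives 88, not 89, and the footnote may be a slip. The contradiction does not depend on the explanation.

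**Conclusion.** The concern holds. Three current sections place the primary PFS analysis at 89 events, and the statistics sections of both documents place it at 93. The stated power, boundary hazard ratio and analysis month all belong to 93. At 89 they become 88.8%, 0.660 and about month 31.5.

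These figures assume the Schoenfeld formula, and the timing also assumes exponential times with uniform accrual. Another events formula would shift the absolute power: under Freedman's, 93 events give 87.9% and 89 give 86.5%. The inconsistency between the two counts would remain.

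The seriousness lies in leaving the trigger for all confirmatory testing ambiguous in an open-label design, not in the 1.3 points of power. As a plan, it had to be corrected before randomization. Because the study ended after 3 subjects, no reported result is affected.

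**What to change.** Replace 89 with 93 PFS events per BIRC in the protocol synopsis, protocol 4.1.2 and SAP 3.1.2. Correct the Table 21 footnote from HR 0.5 to HR 0.51 so that it agrees with its row.

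If 89 was in fact intended, change 93 to 89 throughout protocol 11.3.1, Tables 21 and 22, and SAP 5.1 and 5.2, and restate the power as 88.8%, the boundary hazard ratio as 0.660 and the expected timing as about month 31.5.

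The first option costs a wording change in three places and one footnote. It needs no additional subjects and no redesign.

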4.2. Endpoints

4.2.1. Primary Endpoints

The primary endpoint of the study is

- For Part 1, safety as measured by incidence of CRS and TEAEs; and
- For Part 2, PFS, defined as the time from randomization to first documentation of progressive disease or death, whichever comes first, as assessed by the BIRC using Lugano 2014 criteria.

4.2.2. Secondary Endpoints

The secondary endpoints of the study are as follows:

1. Best ORR and CRR, as assessed by Investigator and by the BIRC according to Lugano 2014 criteria (Cheson, 2014)

2. OS, defined as the time from randomization to death from any cause
3. TTF, defined as the time from randomization to discontinuation of all study treatment for any reason, including disease progression (as assessed by Investigator and by BIRC), treatment toxicity, and death, whichever comes first
4. DOR, defined as the time from first response to progression or death due to any cause, whichever comes first, among subjects achieving an objective response (OR) and among subjects with CR as assessed by BIRC
5. PFS, as assessed by Investigator using Lugano 2014 criteria
6. Incidence, timing, and severity of CRS as assessed by following CRS-related AEs, including incidence and grade of AEs and incidence of SAEs, with CRS grading defined by the ASTCT Consensus Grading
7. Incidence, timing, and severity of neurological AEs, and incidence and grade of Immune Effector Cell-Associated Neurotoxicity Syndrome (ICANS)
8. Dose intensity of tafasitamab and lenalidomide as measured by planned and actual dose administration in Part 1
9. Incidence and severity of TEAEs in Part 2, with severity defined by the National Cancer Institute (NCI)-Common Terminology Criteria for Adverse Events (CTCAE) version 5.0

4.2.3. Exploratory Endpoints

The exploratory endpoints of the study are as follows:

1. PK concentrations of plamotamab and tafasitamab
2. Anti-plamotamab and anti-tafasitamab antibodies
3. Absolute counts and percentage change from baseline in measurements of B-, T-, and natural killer (NK) cell populations
4. Analyses of exploratory and diagnostic biomarkers (including, but not limited to, cell of origin by Hans algorithm [germinal center B-cell (GCB) versus non-GCB], CD10, CD19, CD20, MUM1, BCL2, and BCL6 expression); peripheral and intratumoral leukocyte frequencies, phenotyping, functional and activation markers at baseline and on treatment; gene expression profiling for cell of origin subtyping and exploratory transcriptomic analysis, and genomic analysis in tumor including, but not limited to, FcR genotyping and MRD ctDNA analysis in blood
5. Rituximab concentrations at baseline
6. Biomarkers of CRS; eg, serum cytokine levels

7. Randomization strata and baseline characteristics subgroup analyses of ORR, PFS, OS and TTF

4.3. Treatment Regimens

This study consists of 2 parts:

- Part 1: single-arm, two-cohort, safety run-in
- Part 2: open-label, randomized, two-arm efficacy and safety

4.3.1. Part 1: Single-Arm, Safety Run-In

Part 1 is a single-arm, two-cohort, safety run-in intended to establish the safety of the combination of plamotamab, tafasitamab, and lenalidomide.

Treatment consists of the combination of plamotamab, tafasitamab, and lenalidomide administered in 28-day cycles, with 2 priming doses of tafasitamab before Cycle 1. Plamotamab and tafasitamab can be administered until disease progression, unacceptable toxicity, or discontinuation for any other reason, whichever comes first; however, lenalidomide can be given for only up to a total of 12 cycles. Tafasitamab and plamotamab must not be administered simultaneously. On days when both tafasitamab and plamotamab are given, the tafasitamab should be given first followed by plamotamab. It is recommended that the infusions are separated by at least 2 hours.

4.3.2. Part 2: Open-Label, Randomized

Part 2 is an efficacy cohort where subjects are randomized to receive Arm A or Arm B as follows:

Arm A:

[figure not shown]
Treatment consists of the combination of plamotamab, tafasitamab, and lenalidomide administered in 28-day cycles, with 2 priming doses of tafasitamab before Cycle 1. Plamotamab and tafasitamab can be administered until disease progression, unacceptable toxicity, or discontinuation for any other reason, whichever comes first. Lenalidomide can be given for up to a total of 12 cycles.

Arm B:

Treatment consists of the combination of tafasitamab and lenalidomide administered in 28-day cycles with 2 priming doses of tafasitamab before Cycle 1. Tafasitamab can be administered until disease progression, unacceptable toxicity, or discontinuation for any other reason, whichever comes first. Lenalidomide can be given for up to a total of 12 cycles.

Part 1 and Part 2 dose and schedule are presented in the schematic below ([Figure 2](#)):

Figure 2: Dosing Schema

4.4. Number of Subjects

Part 1 will enroll at least 40 subjects into 2 cohorts with a minimum of 20 subjects per cohort.

Part 2 will enroll approximately 200 subjects. The sample size for Part 2 may be adjusted based on the results from Part 1. Any increase in the enrollment number beyond 200 will be made by a protocol amendment prior to the initiation of the randomized portion. Primary refractory enrollment will be limited in Part 2 to 36 of 200 subjects.

Overall, the study is planned to enroll approximately 240 subjects.

4.5. Treatment Assignment

Treatment assignment for Part 1 and randomization for Part 2 will be performed via a third-party randomization and trial supply management (RTSM)/interactive response technology (IRT) system.

4.5.1. Part 1: Single-Arm Safety Run-In

During the Part 1 safety run-in, 40 subjects will be enrolled and treated with plamotamab and tafasitamab plus lenalidomide (ie, single-arm, uncontrolled). The subjects will be considered enrolled if they have signed the informed consent, are determined to be eligible, and receive the Day -8 tafasitamab priming dose.

4.5.2. Part 2: Open-Label Randomized

During Part 2, a total of 200 subjects will be randomized as follows: with a 1:1 ratio of plamotamab and tafasitamab plus lenalidomide versus tafasitamab plus lenalidomide, stratified by IPI risk score at baseline (3 – 5 versus 0 – 2); number of lines of prior therapy (1 versus ≥ 2); and primary refractory (yes versus no). A maximum of 36 primary refractory subjects may be enrolled. Subjects will be randomized only if they have signed the informed consent and are determined to be eligible. The initiation of study treatment will occur within 72 hours of randomization. Study treatment will begin on Study Day -8 with the tafasitamab priming doses.

No blinding is specified given the potential for overlapping toxicities. In the presence of overlapping toxicities, a blinded study may result in dose modifications or reductions of placebo. This may confound the management of toxicities without addressing the source of the toxicity through dose modification or reduction schemes. Therefore, to ensure the safety of subjects, the study will not be blinded.

4.5.3. Subject Screening and Enrollment Numbers

Subjects who consent for the study will be assigned a **Subject Screening Number**, a site sequential 8-digit number. The first 3 numbers designate the site number then hyphen, then 5 more numbers for the subject number beginning with 9 for screening (ie, 101-90001).

Subjects who will be eligible to receive study treatment (Part 1) or be randomized (Part 2) will be assigned a **Subject Enrollment Number**, a study sequential 8-digit number, first 3 numbers for the site number, then hyphen, and then 5 more numbers for the subject number (ie, 101–10001).

4.6. Management of Toxicities

The combination of plamotamab, tafasitamab and lenalidomide has not yet been tested in humans. Safety data are available for plamotamab and for the combination of tafasitamab and lenalidomide. Important and potentially overlapping toxicities have been identified and are outlined below. However, new toxicities of the 3-drug regimen may be identified during this study, and investigators should be diligent in the monitoring and management of subjects during treatment. Management of known toxicities such as CRS, infusion-related reactions, hematologic toxicities, and tumor lysis syndrome are outlined by treatment regimen in the following sections.

4.6.1. Cytokine Release Syndrome

The ASTCT defines CRS as “a supraphysiologic response following any immune therapy that results in the activation or engagement of endogenous or infused T cells and/or other immune effector cells. Symptoms can be progressive, must include fever at the onset, and may include hypotension, capillary leak (hypoxia), and end organ dysfunction” (Lee, 2019).

CRS can present with a variety of symptoms ranging from mild, flu-like symptoms to severe life-threatening manifestations of the inflammatory response. Mild symptoms of CRS include fever, fatigue, headache, rash, arthralgia, and myalgia. More severe cases are characterized by hypotension as well as high fever and can progress to an uncontrolled systemic inflammatory response with vasopressor-requiring circulatory shock, vascular leakage, disseminated intravascular coagulation, and multi-organ system failure (Shimabukuro-Vornhagen, 2018). CRS is more likely to occur after the first dose of plamotamab than subsequent doses, tends to begin somewhat later than hypersensitivity reactions, and is more likely to be associated with hepatic and neurologic complications. Plamotamab associated CRS Symptoms observed in the Phase 1 study include:

- Aphasia or word-finding difficulty
- Arthralgia
- Confusion/mental status changes/delirium
- Serum creatinine increase
- Diaphoresis
- Dizziness
- Dyspnea
- Fatigue (asthenia, lethargy, malaise)
- Fever
- Gait disturbance/dysmetria
- Headache
- Hypotension/hypertension
- Hypoxia
- Myalgia
- Nausea/vomiting
- Rigors/chills
- Tachycardia
- Tachypnea
- Seizures
- Transaminitis/hyperbilirubinaemia
- Tremor

CRS toxicity is defined using the ASTCT CRS Consensus Grading (Lee, 2019). See Table 4 for these definitions.

Table 4: American Society for Transplantation and Cellular Therapy Cytokine Release Syndrome Consensus Grading

CRS Parameter	Grade 1	Grade 2	Grade 3	Grade 4
Fever ^a	Temperature ≥ 38 °C	Temperature ≥ 38 °C	Temperature ≥ 38 °C	Temperature ≥ 38 °C
		With		
Hypotension	None	Not requiring vasopressors	Requiring a vasopressor with or without vasopressin	Requiring multiple vasopressors (excluding vasopressin)
		And/or ^b		
Hypoxia	None	Requiring low-flow nasal cannula ^c or blow-by	Requiring high-flow nasal cannula ^c , facemask, nonrebreather mask, or Venturi mask	Requiring positive pressure (eg, CPAP, BiPAP, intubation and mechanical ventilation)

BiPAP = bilevel positive airway pressure; CPAP = continuous positive airway pressure; CRS = cytokine release syndrome; CTCAE = Common Terminology Criteria for Adverse Events.

Organ toxicities associated with CRS may be graded according to CTCAE v5.0, but they do not influence CRS grading.

^a Fever is defined as temperature ≥ 38 °C not attributable to any other cause. In subjects who have CRS then receive antipyretic or anticytokine therapy such as tocilizumab or steroids, fever is no longer required to grade subsequent CRS severity. In this case, CRS grading is driven by hypotension and/or hypoxia.

^b CRS grade is determined by the more severe event: hypotension or hypoxia not attributable to any other cause. For example, a subject with temperature of 39.5 °C, hypotension requiring 1 vasopressor, and hypoxia requiring low-flow nasal cannula is classified as Grade 3 CRS.

^c Low-flow nasal cannula is defined as oxygen delivered at ≤ 6 L/minute. Low flow also includes blow-by oxygen delivery, sometimes used in pediatrics. High-flow nasal cannula is defined as oxygen delivered at > 6 L/minute.

Source: Lee, 2019.

